10. Any chronic or acute illness or psychiatric conditions that would impact adherence to the study requirements

Sample Size

A total of 20 patients will be recruited from chronic pain patients hospitalized at Wake Forest Baptist Health Main Campus

Interventions and Interactions:

- A. The chronic pain Advanced Practice Provider will evaluate the patient and determine if and when they can be included in the study. If the patient is determined to be eligible, the participant will be consented by a study team member prior to collection of any study data.

Baseline

- Review the home dose of opioid w/ participant collecting type, frequency and milligram use and date and time of last use prior to admission.
- A study team member will provide the participant with the study questionnaire packet as well as instructions for completing the questionnaires.
- Participants will be informed of the reminders that they will receive to complete the questionnaires twice a day for three days (i.e., verbal reminder from staff, signage placed in the room). Participant contact information will be collected to ensure appropriate and timely follow up.
- A study team member will perform the pain score assessment with the participant to establish baseline pain score.
- The participants will be asked to complete baseline questionnaires prior to the initiating placement of the acupressure including: Discomfort on Initiation of Acupressure (on 0-10 NRS scale), Pain Intensity, Enjoyment, General Activities Scale (PEG), Pain Catastrophizing Scale (PCS), Generalized Anxiety Disorder Scale (GAD-7), Patient Global Impression of Change Scale (PGIC) (only collected after Acupressure applied) and PROMIS sleep disturbance scale.

Day 1

The Baseline and Day 1 visits can take place on the same day.

Following completion of baseline questionnaires, the trained Auricular Acupressure nurse will place the acupressure pads and instruct the participant how to do acupressure three times daily for 3 days.

- o If the ear contains lesions, skin breakdown, or show signs of irritation, the acupressure pads will not be placed, and this will be noted in the study record.

- If the participant consented to the recording portion of the study, they will be reminded of the process and the acupressure nurse will confirm that the participant still agrees to participate in the recording portion of the study.

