Each study participant will be asked to sign a separate consent giving permission for the intervention to be recorded and used for educational and research purposes. The recordings will be done to limit exposure of the study participant’s face.

The interventionist's time will be measured in minutes from time the interventionist enters room to place acupressure pads to when the interventionist exits room. Qualitative questions will be used to assess overall feasibility.

- The study team will perform the pain score assessment with participants (on 0-10 NRS scale) two (2) times a day for 3 days. If the study team is unable to perform the pain scores assessment in person, we will use the pain score that has been assessed by the clinical team as part of their regular care and documented in the participant's medical record.

Study participants will be reminded to complete their daily study activities.

- A member of the study team will remind the participant to complete their assessment(s) or the study nurse can place an order in Wake One to prompt the care team to remind the participant.
- A sign will be placed in the participant's room reminding them to complete their study activities.

Monitoring opioid usage: data abstraction will be done and verified in Wake One if the participant remains inpatient for the 3 days.

End of Study Assessment:

Within 24 hours of the completion of the assessments and the removal of the acupressure beads, a member of the study team will assess patients'

- Pain scores
- Opioid medication frequency and dosage
- Verify completion of Day 3 study questionnaires: Pain Catastrophizing Scale (PCS); Generalized Anxiety Disorder Scale (GAD-7); Pain, Enjoyment, General Activities Scale (PEG); Patient Global Impression of Change Scale (PGIC); PROMIS sleep disturbance scale

Participant will also be asked to complete "Willingness or desire to decrease opioid dependence and usage" and Acupressure Acceptability questionnaires on Day 3

Outcome Measures:

Since this is a feasibility study, results will be analyzed initially using descriptive statistics of main outcome measures.

To evaluate the efficacy of the auricular acupressure the following outcomes will be assessed:

Primary Outcomes:

Patient reported pain scores – change in patient reported pain scores (derived from the NRS and PEG scale) from baseline and Day 1-Day 3.

Secondary Outcomes to be measured:

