Willingness or desire to decrease opioid dependence and usage (Assessed using Likert Scale). Assessment of patient's willingness or desire to decrease opioid dependence and usage will be assessed through having the patient answer by stating (1) Strongly disagree; (2) Disagree; (3) Neither agree nor disagree; (4) Agree; (5) Strongly agree to determine patients with a higher score denoting a greater willingness to decrease dependence.

BAA Press placement survey (interventionists only)

The Interventionist's (Acupressure nurse) will be asked to capture time related to completion of study tasks and other qualitative questions to assess overall feasibility.

Additional Data collection: contact information, relevant demographic data that will be recorded are DOB, age, gender identity, sex at birth, BMI, ethnicity/race, educational level, employment status, relationship status, disability insurance status and socioeconomic status. Relevant medical history will be duration of narcotic use (in years) and comorbid pain syndrome diagnoses.

Study activity	Baseline ^a	Day 1	Day 2	Day 3/ end of study
Informed Consent signed	X			
Review the home dose of opioid w/ participant	X			
Complete data collection form	X	X	X	X
Distribute Participant Questionnaire and review completion instructions	X			
Administer or record Pain score assessment (NRS) ^b	X	X	X	X
Questionnaire completion reminder ^c		X	X	X

Pain Catastrophizing Scale (PCS)	X			X
Pain, Enjoyment, General Activities Scale (PEG)	X			X
Patient Global Impression of Change Scale (PGIC)	X			X
PROMIS sleep disturbance scale	X			X
Generalized Anxiety Disorder Scale (GAD-7)	X			X
Acupressure placement and patient education		X		
*Optional interventionist recording of AA placement ^d		X		
Willingness or desire to decrease opioid dependence and usage questionnaire				X
Acupressure Acceptability questionnaire				X
Study team collect completed questionnaire				X
Compensation administration				X

BAA press placement survey (interventionist only)	X	X	X	X
---	---	---	---	---

^a Baseline and Day 1 can be completed on the same day. Baseline activities are to be completed prior to Acupressure administration

^b The study team will perform the pain score assessment with the participant two times a day for three days. If the study team is unable to perform the pain scores assessment in person, the pain score that has been assessed by their clinical team as part of their regular care will be pulled

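### Two instruments are scheduled before the acupressure they are meant to rate; the Day 1 NRS order and the choice of Day 3 value also need stating

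*Combined protocol and SAP*

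**What the plan says.** **Instruments.** The Baseline part of Interventions and Interactions asks participants to complete a set of questionnaires before the pads are placed. The first in the list is a 0-10 rating of discomfort on starting acupressure. PGIC is in the same list, with a parenthesis restricting it to after application. In the study activity table PGIC has a mark at Baseline and another at Day 3, and the discomfort rating has no row. Footnote a to the table says: "Baseline activities are to be completed prior to Acupressure administration".

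**NRS.** The primary outcome is "change in patient reported pain scores (derived from the NRS and PEG scale) from baseline and Day 1-Day 3". The baseline score is covered by "A study team member will perform the pain score assessment with the participant to establish baseline pain score". For follow-up, "The study team will perform the pain score assessment with participants (on 0-10 NRS scale) two (2) times a day for 3 days". If the team cannot attend, "we will use the pain score that has been assessed by the clinical team as part of their regular care". Footnote b to the table repeats both rules. On the calendar, "The Baseline and Day 1 visits can take place on the same day".

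**End of study.** Pads come off once Day 3 activities are finished. The End of Study Assessment section then has pain scores assessed within 24 hours of completing the assessments and removing the beads. The table has one combined column for Day 3 and end of study, with one NRS mark.

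**The concern.** A rating of discomfort at initiation, or of change since treatment, has nothing to refer to if it is taken before the pads are on. In a feasibility trial, how placement is tolerated is a result of direct interest. A form filled in at the wrong time loses that information or returns meaningless values. A PGIC completed before treatment also invites someone later to treat it as a baseline for change, which it cannot be.

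The NRS question is about definition. The Analytical Plan says the data will supply parameter estimates for powering later studies. If it is not fixed which readings are follow-up and which one is the Day 3 value, two analysts can derive different changes from the same 20 patients. A Day 1 reading taken before placement would also make the summary depend partly on when the nurse arrived.

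**Working it through.** The plan gives no figure to reproduce, so the check is mainly a side-by-side reading.

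**1. Discomfort rating.**
- Baseline section: in the list completed before placement, with no exception.
- Study activity table: no row, so nothing corrects the timing.
- Result: as written, it is completed before there is any acupressure to rate.

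**2. PGIC.**
- Baseline section: only after acupressure has been applied.
- Table: marks at Baseline and Day 3. Footnote a puts Baseline activities before acupressure.
- End of Study Assessment: PGIC is among the Day 3 questionnaires.
- Result: the Baseline mark contradicts the narrative; the Day 3 mark agrees with it.

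**3. Day 1 NRS.**
- Footnote a orders baseline activities only, not Day 1 readings.
- Placement has no set hour, and Day 1 may be a different day from baseline, so one of that day's two readings can come first.
- The chart-score substitute has no time window and no condition that it follow placement.
- On a same-day start, separate marks for Baseline and Day 1 suggest two distinct scores, but no sentence says the baseline score may not serve as a Day 1 reading.

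**4. Day 3 value.**
- Two readings are due on Day 3, and the secondary outcomes refer to am and pm scores. No rule picks one or combines them.
- The End of Study Assessment wording reads like a further score after removal, but the single table mark allows it to be the Day 3 score. The text settles neither.
- The opioid outcome does name its end point (a Day 3 post evaluation); the pain outcome does not.

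**5. Scale of point 3, for illustration only.** Assume an equal-weight mean of the 2 × 3 = 6 follow-up readings, a constant effect after placement and none before. None of these assumptions is in the plan. If a share f of patients have one pre-placement reading, the fraction of the mean change kept is (6 − f)/6:

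| f | Kept | Loss |
|---|---|---|
| 1 | 5/6 = 0.833 | 16.7% |
| 0.5 | 5.5/6 = 0.917 | 8.3% |
| 0.25 | 5.75/6 = 0.958 | 4.2% |

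For a change from baseline to the scheduled Day 3 NRS the loss is 0%, because pads are due to stay on until Day 3 activities are complete. PEG is collected only at Baseline and Day 3, so the Day 1 question cannot reach it.

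**The case against.** The best defence is that the intended NRS order is clear enough. The Day 1 section opens with placement straight after the baseline questionnaires, the twice-daily NRS is described after the placement steps, and the table separates the Baseline and Day 1 marks. The natural reading is that Day 1 scores follow placement. In addition, the data collection form and the participant questionnaire (Appendices A and G) are listed by title only; they may already carry score times, am and pm slots, or the discomfort item in its proper place.

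Most of this stands, and it reduces the NRS point to a clarification. It does not fully dispose of it: the order of paragraphs is not a timing rule, and it cannot govern scores charted by ward staff as part of routine care.

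For PGIC, the defence is that the narrative parenthesis and the Day 3 list show the intent. That also stands, so this is an inconsistency to reconcile and not evidence of a planned pre-treatment PGIC. The discomfort rating has no such defence in the visible text.

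**Conclusion.** Minor. The two instrument errors can be read directly off the page and depend on no assumption: the discomfort rating is placed before the event it rates, and the PGIC Baseline mark contradicts the Baseline section. Neither affects the pain estimate.

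The NRS points are missing detail. The visible text does not state that Day 1 readings follow placement, puts no time window on chart scores, and does not say which reading is the Day 3 value or whether the end-of-study score is separate from it.

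A reader might infer that the primary pain change is diluted by untreated Day 1 readings, or by scores taken after removal. The documents do not support that. No averaging rule is stated; the Analysis Plan offers descriptive statistics. A separate post-removal score is only one possible reading, and nothing says such a score would be averaged in. PEG and a change to the scheduled Day 3 NRS are untouched by the Day 1 gap. The 4% to 17% range describes the assumptions in the illustration, not the plan. Even the direction of any effect is uncertain, since inpatient pain can drift for other reasons.

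**What to change.** 1. Collect the discomfort rating right after placement on Day 1, take it out of the pre-placement list, and add a row to the study activity table.
2. Delete the Baseline mark for PGIC so that the table agrees with the Baseline section.
3. State that only Day 1 NRS readings timed after placement count as follow-up, chart scores included, and that the baseline score is not reused as a Day 1 reading. Apply the same rule to the am/pm trajectory.
4. State whether the end-of-study pain score is the Day 3 NRS or a separate time point, and whether the Day 3 value is the am reading, the pm reading or their mean.

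The cost is a corrected table and a few sentences. Placement is already documented in Wake One and the interventionist's time in the room is measured, so a placement time may be recoverable. NRS readings need a recorded time; if Appendix A lacks that field, it must be added. If the forms already settle any of these points, the text need only be brought into line with them. The downside is that patients whose pads are placed late on Day 1 contribute fewer Day 1 readings, mainly pm ones, which leaves the trajectory unbalanced on that day and should be noted when it is reported.

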This feasibility trial is being performed in collaboration with the BAApres Training and Intervention Fidelity study (IRB00084011). Under this grant, individual study teams conduct non-randomized feasibility trials to assess intervention feasibility and provide initial parameter estimates on specified outcomes.

The AA interventionists for this study will complete Auricular Acupressure training modules and complete competency assessments and intervention assessments throughout the study. Study teams will include the possibility that a study participant may be part of a competency assessment and that their session may be recorded and securely uploaded to a server per IRB and Institutional policies.

Objectives:

The purpose of this study is to determine if the addition of auricular acupressure to the typical pharmacological regimen given to patients on the chronic pain/addiction service will lower pain scores and decrease pain medication usage.

Setting:

This will be a study utilizing the location of Atrium Health Wake Forest Baptist (Main Campus) for initiation of study procedures.

Subject selection criteria

Any patient admitted to Atrium Health Wake Forest Baptist for which our chronic pain/addiction medicine service is consulted.

Inclusion:

Patient admitted to the hospital with a chronic pain/addiction medicine service consult.

1. Age > or equal to 18
2. History of documented chronic pain with or without opioid use disorder
 - a. Polysubstance abuse or opioid use disorder
 - b. **Or opioid use (documented as home medication)**
3. Expected length of stay (admission) is at least 5 days at the time of recruitment
4. Able to read and understand the informed consent form

Exclusion:

1. Patient refusal
2. Patients who are at a risk of leaving against medical advice (AMA) during their current admission may be excluded per the investigator's discretion
3. Since this is a feasibility pilot, only English-speaking participants will be eligible.
4. Inability to communicate via telephone
5. Participants with a history of skin disease (e.g., psoriasis) involving the ear, adhesive allergy, recent scar tissue on ear, or current abrasions or cuts on ear,
6. Cognitive impairment (delirium, dementia)
7. Physical impairment preventing them from applying pressure to the beads
8. Patients with cardiac pacemakers (contraindication to POINTER PAL)

9. Use of some types of hearing aids (obstructing the placement of beads)

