Opioid use - Pre-Admission Opioid requirement and change from baseline (medication used during the intervention and as reported afterwards vs. home dose before the study started) collecting type, frequency and milligram use and date and time of last use prior to admission measuring mean/median changes from Baseline to Day 3 post evaluation. Trajectory of am and pm pain scores.

Generalized Anxiety Disorder Scale (GAD-7) – A Self-administered 7 item scale that draws from DSM-V criteria for General Anxiety Disorder (GAD) to identify GAD and measure symptom severity. It is routinely used as a tool to measure longitudinal changes and track treatment progress.

Patients are asked to rate the frequency of anxiety symptoms over the last 2 weeks on a Likert Scale (0-3). In general, patients with GAD or other common anxiety disorders exhibit GAD-7 scores of 10 or greater.

Pain Catastrophizing Scale (PCS) - The assessment of thoughts and feelings of the patients will be assessed using questions that are rated 0 for not at all to 4 for all the time. The Pain Catastrophizing Scale (PCS) assesses the extent of catastrophic thinking due to low back pain according to 3 components: rumination, magnification, and helplessness. It is a 13-item scale, with a total range of 0 to 52. Higher scores are associated with higher amounts of pain catastrophizing.

Composite Pain, Enjoyment and General Activity Scale (PEG) Assessment of pain intensity and interference. We will compare scores before and after initiation of Auricular Acupressure.

Patient Global Impression of Change (PGIC) – patient reported assessment of improvement or decline of their pain

PROMIS Sleep disturbance – patient reported outcome on the quality of their sleep.

Acupressure Acceptability questions - We will ask acceptability questions. "How satisfied were you with how your pain has been treated?" using the Likert scale to measure "Very satisfied =5, Satisfied=4, Somewhat satisfied = 3, Somewhat dissatisfied= 2, Dissatisfied 1, Very Dissatisfied 0. Would you consider using auricular acupressure in the future for pain or if recommended by your nurse or physician? a. No, would not use again (Score of 0) b. Maybe (Score of 1), c. Yes, I would consider using in the future (Score of 2) 3. Is there anything else you would like to tell us that may be helpful for us to know regarding ear acupressure? (Each answer will be collected and assessed for future studies).

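### The opioid outcome does not separate opioids given for pain from opioids given to treat opioid use disorder, so it is broader than the stated objective

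*Combined protocol and SAP*

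**What the plan says.** The Objectives section asks whether adding acupressure "will lower pain scores and decrease pain medication usage".

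Under Subject selection criteria, the source population is "Any patient admitted to Atrium Health Wake Forest Baptist for which our chronic pain/addiction medicine service is consulted". Inclusion criterion 2 requires documented chronic pain, with or without opioid use disorder, and then gives two routes: "Polysubstance abuse or opioid use disorder", and "Or opioid use (documented as home medication").

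Under Outcome Measures, the secondary outcome Opioid use is "Pre-Admission Opioid requirement and change from baseline". The comparison is "medication used during the intervention and as reported afterwards vs. home dose before the study started". The data items are given as "collecting type, frequency and milligram use and date and time of last use prior to admission", and the summary as "measuring mean/median changes from Baseline to Day 3 post evaluation". Indication is not among the items, and no common dose unit is stated.

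The other places that touch opioid data add no separation by purpose. The Baseline review of home opioids lists the same items. Inpatient opioid use is abstracted from the medical record. The End of Study Assessment lists only frequency and dosage. The Analytical Plan describes a single-arm feasibility study of 20, analysed descriptively at first, whose data will supply parameter estimates for powering later studies.

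**The concern.** The objective is about medication for pain, while the outcome covers opioid medication without regard to purpose. In a sample without opioid use disorder the two would nearly coincide. Here patients with that disorder are eligible, and the service that sees them covers both pain and addiction. An opioid given to treat the disorder may therefore be started, raised, lowered or stopped in the same three days. Such a change says nothing direct about analgesic need, yet under the outcome as written it enters the change score in full.

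The comparator adds to the problem. Because the two inclusion routes are alternatives, a participant who enters through opioid use disorder need not have a documented home opioid. If the home dose is then recorded as zero, any treatment started for the disorder counts entirely as an increase.

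With no control group, nothing offsets these changes. Two products of the study are at stake: the reading of the mean or median change as evidence on pain medication, and the mean and standard deviation carried forward to size a later trial.

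**Working it through.** The plan gives no figure for this outcome (no expected change, standard deviation, alpha or power), so there is nothing to reproduce. The check has two parts.

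**1. Text, side by side**

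| Element | What the plan specifies | Separated by purpose? |
|---|---|---|
| Objective | Pain medication | Restricted to pain |
| Eligibility | Opioid use disorder is one of two routes | Not applicable |
| Home opioid review (Baseline) | Type, frequency, milligrams, last use | No |
| Inpatient abstraction | Opioid usage from the record | No |
| End of Study Assessment | Frequency and dosage | No |
| Secondary outcome | Medication used versus home dose, mean/median change | No |
| Analysis Plan | Descriptive statistics first | No |

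The outcome is broader than the objective, and no visible rule narrows it at any later step.

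**2. Illustration of size**

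Only N = 20 comes from the documents. Everything else is an assumption: n participants have a dose d (mg/day, in some common unit) of treatment for opioid use disorder added during the study.

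*Mean.* Shift = (n/20) × d.

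| n | d = 20 | d = 60 |
|---|---|---|
| 1 | 1 | 3 |
| 2 | 2 | 6 |
| 6 | 6 | 18 |

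The range is +1 to +18 mg/day. If the same doses were removed instead of added, the signs reverse: −1 to −18 mg/day.

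*Median.* Because the plan allows either summary, I simulated 20 normally distributed changes with an assumed standard deviation of 15 to 60 mg/day and added d = 60.
- n = 2: the median shifts by about 2 to 5 mg/day (mean: 6).
- n = 6: the median shifts by about 8 to 17 mg/day (mean: 18).

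The median is less affected, but when the spread is wide relative to d the protection is small.

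*Against an assumed true effect.* Suppose pain opioids truly fall by a mean of 10 mg/day. The pooled mean is −10 + n × d/20.
- n = 4, d = 40: −10 + 8 = −2.
- n = 6, d = 40: −10 + 12 = +2.
- The fall is fully cancelled at n = 10 × 20/d, which is 10 participants at d = 20 and 5 at d = 40.

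*Spread.* If a proportion p independently has d added, the extra variance is p(1 − p)d². With d = 60:
- p = 0.10: 0.09 × 3,600 = 324.
- p = 0.30: 0.21 × 3,600 = 756.

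Against an assumed analgesic-change standard deviation of 30 (variance 900), that is a rise of 36% to 84%. Against 60 (variance 3,600), it is 9% to 21%. With d = 20 the extra variance is 36 to 84, which is 4% to 9% of 900. For a fixed target difference, a later trial's sample size scales with the variance.

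**The case against.** **The documents do not say the two uses are summed.** They never mention opioid treatment of opioid use disorder, nor say that the consult service starts or adjusts it during the study days. This stands. Pooling is inferred from the absence of a separating rule, and the clinical scenario from the eligibility criteria and the remit of the service. How often it would occur is unknown.

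**The unseen form may solve it.** Appendix A appears by title only and is completed at every visit, so it could hold an indication field. This stands as a limit. The outcome definition would still need to say how the field is used. Type of opioid is collected, so a later split by drug is partly possible, but drug type need not identify purpose, and a split chosen after seeing the data is weaker than a stated one.

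**Direction.** A reader might infer that the outcome is tilted against acupressure. The documents do not support that. Stopping or lowering treatment that was part of the home dose would look like benefit, so the net direction is unknown.

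**Total opioid use is itself a sensible measure.** The Background wants opioids kept low to avoid CNS and respiratory depression, which concerns exposure whatever the purpose. This stands, and it argues for reporting total use next to the pain measure.

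**Separation does not rescue the comparison.** Everyone enrolled has chronic pain, so dual-purpose drugs may be common. Inpatient use would also still be set against home dose, during admissions when pain is often higher, with no control. Both points stand. Separation removes one source of ambiguity only.

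**Conclusion.** The point holds as a mismatch between objective and outcome. The objective names pain medication; the outcome takes in opioids without regard to purpose, in a sample where the two can differ. Changes in treatment for opioid use disorder would be read as changes in opioid requirement, could move the mean and the median either way, and would add to the spread passed on to later studies.

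The size is unknown. The range of 1 to 18 mg/day in the mean rests wholly on assumed counts and doses and on a common unit that the plan does not state. It shows that a modest number of such changes could matter with 20 participants; it is not an estimate of what will happen.

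This is a secondary outcome with no specified formal test, so the harm is to interpretation and planning estimates. The change should be made, but the trial does not depend on it.

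**What to change.** In the protocol, under Secondary Outcomes (Opioid use) and the Baseline procedures:

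1. Record the order indication for each inpatient opioid, and the purpose of each home opioid at the baseline review. If Appendix A already has such a field, cite it in the outcome definition.
2. State the common unit in which doses are summed.
3. Report change in opioids given for pain as the measure that matches the objective.
4. Report treatment for opioid use disorder as a separate descriptive line: number started, stopped and changed.
5. Report total opioid use alongside.
6. Put drugs with a dual or unclear indication in their own stated category, and show the pain-opioid result with and without them.

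The cost is one extra field per opioid in an abstraction and a baseline review that are already planned, plus some ambiguous classifications, which item 6 makes visible. The change concerns measurement only and proposes no clinical rule.

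### The opioid outcome compares use during and after acupressure only with the pre-admission home dose, so it cannot separate the home-to-hospital shift from the change after pad placement

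*Combined protocol and SAP*

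**What the plan says.** All references are to the combined protocol and SAP.

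- **Objectives.** The study asks whether adding acupressure "will lower pain scores and decrease pain medication usage".
- **Outcome Measures, Secondary Outcomes (Opioid use).** The comparison is "medication used during the intervention and as reported afterwards vs. home dose before the study started", summarised as a mean or median change from Baseline to Day 3.
- **Interventions and Interactions, Baseline.** The one opioid item named is "Review the home dose of opioid w/ participant collecting type, frequency and milligram use", together with when the last dose before admission was taken. For pain, the same section says "A study team member will perform the pain score assessment with the participant to establish baseline pain score".
- **Monitoring opioid usage.** In-hospital use comes from the chart: "data abstraction will be done and verified in Wake One if the participant remains inpatient for the 3 days".
- **End of Study Assessment.** The study team also records how often opioids were taken and at what dose. No condition of remaining in hospital is attached.
- **Subject selection criteria, Inclusion.** "Patient admitted to the hospital with a chronic pain/addiction medicine service consult".
- **Schedule of activities.** The row "Complete data collection form" is marked at Baseline and on Days 1 to 3, but the content of that form (Appendix A) is not shown. Footnote a reads "Baseline and Day 1 can be completed on the same day. Baseline activities are to be completed prior to Acupressure administration".
- **Analytical Plan.** There are 20 participants and no control group. The analysis is descriptive first, and the data are meant to supply parameter estimates for powering later studies.

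**The concern.** Between the home dose and the first pad, each participant has been admitted with an acute problem and referred to the pain/addiction service. Opioid use may already have moved by then. The Background gives reasons for movement either way: pain is often worse on admission, while physicians would rather keep opioids low. A change measured from the home dose includes that movement.

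Pain is treated differently. The NRS has a baseline taken in hospital before placement, and the PEG is compared before and after acupressure starts. Opioid use is the other half of the stated objective, yet its outcome sentence has no corresponding before-and-after comparison.

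Two things are at stake. A reader may take the reported opioid change as what happened after acupressure began. And a mean and SD that include the admission shift could be carried into the power calculation for a later inpatient trial, where they would not describe the quantity of interest.

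**Working it through.** The plan gives no figure to reproduce here. There is no alpha, power, effect size or SD behind the 20 participants, and the point does not depend on them. The check is a decomposition followed by an illustration.

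**Decomposition.** Let H be the home daily dose, P the inpatient use per 24 h before placement, and D the use per 24 h after placement. Then

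D − H = (P − H) + (D − P).

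The left side is the stated outcome. On the right, the first term is the home-to-hospital shift and the second is the change after placement. The outcome sentence names H and D but not P, and no visible section names P as a measurement or comparator. One number cannot recover both terms.

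Example in arbitrary units (assumed): H = 60, P = 120, D = 90. The stated outcome is 90 − 60 = +30. Its parts are 120 − 60 = +60 and 90 − 120 = −30. Use fell after placement, and the outcome reports a rise.

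**Proportional form.** Let R = P/H, and let c be the proportional change after placement, so D = R(1 + c)H. Then

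reported change as a share of home dose = R(1 + c) − 1.

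Both R and c are assumptions; the documents give neither. With c = −0.25:

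| R | R × 0.75 − 1 | Reported change |
|---|---|---|
| 0.5 | 0.375 − 1 | −62.5% |
| 0.8 | 0.60 − 1 | −40% |
| 1 | 0.75 − 1 | −25% |
| 1.25 | 0.9375 − 1 | −6.25% |
| 1.5 | 1.125 − 1 | +12.5% |
| 2 | 1.50 − 1 | +50% |

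The sign flips when R exceeds 1/(1 + c). That is 1/0.75 = 1.33 for a 25% fall and 1/0.90 = 1.11 for a 10% fall. With no change after placement (c = 0), the outcome reads R − 1, for example −20% at R = 0.8. At R = 1 there is no distortion.

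The protocol does not say that change will be expressed as a percentage. On the absolute scale, measured in points of home dose, a fall of 15 after placement appears as −45, −30, −15, 0 or +15 when the shift is −30, −15, 0, +15 or +30.

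**Stability of the added baseline.** Baseline and Day 1 may fall on the same day, so the window before placement can be short. For an assumed 10-unit dose, one dose more or less moves the 24-h rate by 10 × 24/24 = 10 units in a 24-h window, 10 × 24/12 = 20 in 12 h, and 10 × 24/6 = 40 in 6 h.

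**Shorter stays after placement.** A rate handles these directly. For example, 135 units over 36 h is 135 × 24/36 = 90 per 24 h, the same as 270 units over 72 h (270 × 24/72 = 90).

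**The case against.** Several objections carry weight.

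- *The home reference looks deliberate.* The outcome sentence opens with the pre-admission requirement, and change from usual requirement is a fair descriptive question in opioid-tolerant patients. This stands. A reader might infer that the home-dose comparison is wrong and should be replaced or demoted; the documents do not support that. The case is for a second contrast beside it.
- *The data may already exist.* A reader might infer that use before placement is not collected. That cannot be said. The data collection form is completed at Baseline and its content is not shown, and the hospital chart should hold the doses. What can be said is that the outcome as worded does not use them.
- *A pre-placement baseline is not causal either.* Correct. With no control group, change after placement still includes recovery, drug titration and regression to the mean. The gain is a cleaner description.
- *Nothing turns on this outcome.* No test, decision rule or sample size in this study depends on it, which limits the weight of the point. The planned use of the data to power later studies keeps it from being purely cosmetic.
- *Early discharge.* The chart abstraction is conditional on three inpatient days, and a reader might infer that patients discharged sooner have no opioid outcome. The End of Study Assessment plans a reported value without that condition, and eligibility requires an anticipated stay of five days or more. Only a charted value is unstated, so this is a detail of the fix and not a separate defect.

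**Conclusion.** The concern holds as a point about how the outcome is defined. The stated opioid change is the sum of the home-to-hospital shift and the change after placement. It cannot separate them, and its sign can differ from that of the change after placement. This follows from the outcome sentence, the inpatient population and the absence of a control group; no numerical assumption is needed.

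The size is unknown. The illustrative results rest on assumed values of R and c. The documents do not say which way the admission shift runs, so a claim that the outcome is biased towards or against acupressure would go beyond them. How often the sign would reverse in individuals, or whether it would in the cohort mean or median, is also unknown.

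The consequence is modest: a secondary, descriptive outcome in a 20-patient uncontrolled feasibility study. The change is worth making because it is cheap and because it bears on half of the objective and on any opioid estimates carried forward. Confidence is high about the wording, and lower about whether the needed data are already being collected.

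**What to change.** Keep the change from home dose as stated. In Secondary Outcomes (Opioid use), add a second descriptive contrast, for example:

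*Change after placement: charted inpatient opioid use per 24 h from pad placement to Day 3, with the Day 3 value also shown, minus charted inpatient use in the 24 h before placement, both in one common equivalent unit.*

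Specify with it:

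- Where either window is shorter, express use as a rate over the observed hours and report the window lengths.
- For patients discharged before Day 3, use their charted inpatient time in this contrast. Their reported use at the end-of-study assessment stays in the home-dose contrast.
- Label the result as change after placement, not as an acupressure effect.
- When opioid parameter estimates are taken to a future inpatient trial, use this contrast rather than the home-dose one.
- Confirm whether the data collection form already captures use before placement, and add the item if it does not.

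The cost is a sentence or two of outcome wording and up to one more day of chart abstraction for about 20 patients, from a record already being abstracted. There are two downsides. The window before placement may be short or unrepresentative when placement follows soon after admission. A baseline taken while pain is raised may also favour an apparent fall. Both should be stated beside the result.
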